Dependent variables collected postoperatively were obtained daily throughout all phases of the dosing and maintenance phases and included the number of episodes of fecal soiling per day, frequency and severity of abdominal pain and pain associated with antegrade flush administration measured using the WBFPRS as the age appropriate visual analog, and the presence of flush associated vagal symptoms. Serum electrolytes and stool for were calprotectin collected at the end of each dosing phase. Total flush volume was recorded with each flush and measured in mL. Direct parental observation with event recording was used to track and tally soiling episodes defined as non-toilet elimination. Dependent variables were measured and recorded by the parent using a data collection sheet specifically designed for this study. The parent was requested to call if the child was having accidents, discomfort greater than a 4 on the WBFPRS associated with the antegrade flush, or vagal symptoms. The investigator documented any event that could potentially cause a change in level, stability, or trend of the dependent variable not related to the intervention (i.e. initiation of antibiotics or an intercurrent illness).

Materials

Each child had a low-profile button in place to ease flush administration. A cabinet was identified in the clinic space for storage of the flushing solution with continuous temperature monitoring using a MCC

USB 501-LCD thermometer. The cabinet was locked with restricted key access. The temperature in the storage cabinet was consistently maintained between 15 and 30 degrees Centigrade. A temperature monitoring log was completed daily. No ambient temperature excursions occurred. Flush solution type, volume dispensed, lot numbers, and flush solution dispensing time and date were recorded in a dispensing log.

High Volume Flush

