Following successful completion of the dose-response phase, patients were randomized for a second time to either a saline-glycerin-saline or a glycerin-saline-glycerin sequence. The maintenance phase of the study began by administering the established effective dose and frequency of administration for the first flush in the sequence. The child remained on treatment for 4 weeks. The treatment was withdrawn. The child was subsequently placed on the next treatment in the sequence at the pre-established effective dose and frequency for 4 weeks. The second flush was then withdrawn and the initial flush in the sequence was reintroduced for an additional two weeks. If the child experienced recurrence of fecal incontinence or discomfort greater than a 4 on the pain scale, they were dropped from the study. If they successfully completed the maintenance phase, the child was placed on the flushing regimen of his/her choice at the dose and frequency of administration that maintained continence.

Specimen Collection

A stool sample for calprotectin was obtained during the baseline phase prior to any pre-operative bowel prep and additional stool samples were obtained at the completion of each dosing phase for a total of 3 samples. Blood samples for electrolytes were drawn preoperatively and postoperatively at the end of each dosing phase at the time stool samples were obtained for a total of three samples. Funding was secured. Accounts were set up with an outside lab for processing blood samples for electrolyte determination and a second outside lab for processing stool samples for calprotectin.

Statistical Analysis

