This study was a within subjects design with all subjects demonstrating consistent fecal incontinence at baseline and sufficient intervention and post-intervention data points to allow for time series analysis. Data points were graphed on an equal interval 2:3 ratio ordinate and abscissa scale line graph to prevent data distortion during visual analysis. Dependent measures were graphed on the ordinate scale with time-by-day graphed on the abscissa scale. Independent variable effects on target behaviors were analyzed using well established single-case methodology (Gast, 2010; Hartmann et al., 1980; Ma, 2006; Kazdin, 2011; Portney & Watkins, 2009). Clinicaltrials.gov is not configured to allow reporting outcomes from most methods of within subjects data analysis. Reported data was limited to the results from numeric descriptive and inferential analysis that could be adapted to the Clinicaltrials.gov format.

In addition to single-case analytic methodology, descriptive and inferential analysis was used to compare interventional effects and increase the reliability of visual methods analysis. Both the dosing and maintenance phase of the study constituted a 2-treatment crossover design with each child receiving both treatments in both interventional phases of the study (Portney & Watkins, 2009). Descriptive statistics included mean, median, range and standard deviation. A cross-over design compares two treatment sequences; therefore, the groups are independent (Chow & Liu, 2014). Of concern, carry over and direct-by-period interaction is a potential confound with cross-over designs, which if present, could bias treatment effects (Jones & Kenward, 2003; Senn, 2002; Shuster, 2007). The decision was made to use a two-tailed, two-sample pooled variance t-test to lend precision in the presence of carry over effects, and precision and accuracy in the presence of unequal sample size (Shuster, 2009). Significance level was set a priori at 0.05. Effect size was used to determine the magnitude of the treatment difference (Polit, 2010; Rempher & Silkman, 2007).

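### Maintenance soiling and pain are both outcomes and grounds for removal, yet no removal counts as a result; if any child was dropped, the crossover t-test on them is distorted

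*Combined protocol and SAP*

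**What the plan says.** Measures lists the daily outcomes for both the dosing and maintenance phases. They include "the number of episodes of fecal soiling per day, frequency and severity of abdominal pain", together with pain during the flush and vagal symptoms. Treatment failure and removal from the study are not among them.

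High Volume Regimen and Low Volume Regimen keep a child out of maintenance if continence, or tolerable discomfort, could not be reached on a flush. Regimen Maintenance Phase then re-randomises the remaining children to one of two three-period sequences (4, 4 and 2 weeks) and adds: "If the child experienced recurrence of fecal incontinence or discomfort greater than a 4 on the pain scale, they were dropped from the study". It allows for children who do not finish: "If they successfully completed the maintenance phase" is a condition.

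Statistical Analysis treats both phases as two-treatment crossovers, "each child receiving both treatments in both interventional phases of the study". It reasons that "A cross-over design compares two treatment sequences; therefore, the groups are independent" and names the test: "The decision was made to use a two-tailed, two-sample pooled variance t-test". It gives no analysis set, no rule for a dropped child and no failure count. Single-case graphs by day accompany the test, but "Reported data was limited to the results from numeric descriptive and inferential analysis that could be adapted to the Clinicaltrials.gov format".

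**The concern.** A child who relapses on a flush is the clearest evidence that the flush does not hold continence. Under the drop rule that child leaves at the moment the evidence appears. A comparison of mean soiling or pain among children still on study therefore selects on the outcome being compared. Pooling variances and allowing for unequal group sizes do not correct for that.

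Three things that determine the effect are unstated:

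- **Who entered the t-test.** A crossover comparison across two sequence groups needs a value on each flush from each child, so a set with data in both periods is implied. That is an inference; the text does not say it.
- **What counts as recurrence.** In the dosing sections a single report of soiling triggers an adjustment. The maintenance section speaks of recurrence and gives no number of episodes.
- **Whether anyone was gated out or dropped.**

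At stake is the reading of the maintenance result. If children were dropped, a finding of no difference in soiling could not be taken as equal ability to maintain continence. The dosing-phase comparison, electrolytes and calprotectin are outside this point, because the drop rule applies only in maintenance and the specimens are taken at the end of each dosing phase.

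**Working it through.** The documents give no sample size, event rate, SD or number dropped, so there is no stated figure to reproduce. **Every risk below is an assumption.** The two 4-week (28-day) periods from Regimen Maintenance Phase are used. Let a and b be the 4-week chances of at least one soiling episode on the worse and the better flush.

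**1. One episode means a drop; only children with both full periods are used.** Every such child has zero soiling on both flushes. All within-child differences are 0 and the pooled SD is 0, so t = 0/0. Running the test on 6 versus 6 zeros returns no value. This holds whatever a and b are.

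Share leaving before both periods are complete = 1 − (1 − a)(1 − b):

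- 0% vs 0%: 0
- 10% vs 5%: 1 − 0.90 × 0.95 = 14.5%
- 20% vs 10%: 1 − 0.80 × 0.90 = 28%
- 40% vs 10%: 1 − 0.60 × 0.90 = 46%

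With equal allocation at 40% vs 10%, (40% + 10%)/2 = 25% of children leave in period 1 with no data on the second flush.

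**2. One episode means a drop; partial second periods are kept.** Take a constant daily probability h = 1 − (1 − risk)^(1/28). For 40% and 10%, h = 0.01808 and 0.00376. True difference = 28 × (0.01808 − 0.00376) = 0.40 episodes per 28 days.

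Every child who starts period 2 had zero soiling in period 1. The crossover estimate is therefore half the period-2 difference between flushes.

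- Episode counts (at most one per child): ½ × (0.40 − 0.10) = **0.15**.
- Averaged daily rates (an event on day t counts as 1/t): the sum over t = 1 to 28 of h(1 − h)^(t−1)/t is 0.0640 and 0.0144, so ½ × 28 × (0.0640 − 0.0144) = **0.69**.

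The same data understate or overstate the truth according to an unstated choice of summary.

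**3. Two episodes are needed for a drop; both full periods are used; children alike.** Take Poisson counts with mean m = −ln(1 − p), where p is the chance of *at least one episode*, not of recurrence. A child who stays has 0 or 1 episode, with mean m/(1 + m). Recurrence risk = 1 − e^(−m)(1 + m).

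| p, worse vs better | True difference | Difference among stayers | Shrinkage | Recurrence risk | Leave before both periods end |
|---|---|---|---|---|---|
| 40% vs 10% | 0.511 − 0.105 = 0.405 | 0.338 − 0.095 = 0.243 | 40% | 9.4% vs 0.5% | 10% |
| 30% vs 10% | 0.357 − 0.105 = 0.251 | 0.263 − 0.095 = 0.168 | 33% | 5.0% vs 0.5% | 6% |
| 10% vs 5% | 0.105 − 0.051 = 0.054 | 0.095 − 0.049 = 0.047 | 14% | 0.5% vs 0.1% | 0.6% |

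The label matters. If 40% vs 10%, 30% vs 10% and 10% vs 5% were instead the risks of recurrence (two or more episodes), the shrinkage would be 73%, 69% and 52%.

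**4. Pain.** A child who stays can have no discomfort score above 4, so the retained scores are cut off at that value. The effect on the difference depends on the spread of scores on each flush, which the documents do not give.

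**The case against.** The strongest reply is that the problem may never have arisen. The document is written in the past tense. "each child receiving both treatments in both interventional phases of the study" can be read as a report of what happened, and the same section says that all subjects had enough data points for time-series analysis. On that reading no child was lost in the first maintenance period, which is the most damaging kind of loss. This stands as a possibility. It does not settle the matter, because the sentence also reads as a description of the design, and the maintenance section makes completion conditional.

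A reader might go further and infer that children were dropped, that their data were discarded, and that the t-test concealed a real difference. The documents support none of these steps. No passage reports a drop or an exclusion. The bias need not run towards no difference: averaged daily rates gave 0.69 against a true 0.40. A 0/0 statistic would also be visible to the analyst and would not pass as a null p-value.

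The t-test is also additional to the single-case analysis, and daily graphs could show a relapse up to the day of the drop. That is a partial safeguard, but the graphs do not feed the t-test. Because "Reported data was limited to the results from numeric descriptive and inferential analysis that could be adapted to the Clinicaltrials.gov format", someone reading only the registry posting might not see them. The posting is not available here, so it cannot be said that drop counts were left out.

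For pain the effect may be small. In simulations with equal spread on the two flushes, the difference shrank by 0.2% to 7% when under 10% of children left. It could vanish, reverse or widen only in selected settings with very unequal spread, which nothing in the documents supports.

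**Conclusion.** The point holds as a conditional one, with medium confidence. On the text alone, the same two variables are outcomes and removal criteria, removal is not counted, and the stated premise of the crossover is not guaranteed by the entry gate or the drop rule. If at least one child was dropped in maintenance, the t-tests on soiling and pain are distorted.

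For soiling, the consequence ranges from an undefined test, through shrinkage of 14% to 40% in the two-episode cases with children alike, to an estimate of 0.15 or 0.69 against 0.40 when partial second periods are kept. These sizes rest on assumed risks, a constant daily probability or Poisson counts, and an assumed analysis set. They show what the unstated choices can do and are not estimates for this trial. No size is claimed for pain.

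If no child was dropped, there is no such bias. The conclusion that the reported maintenance comparison is wrong is therefore not supported; what is supported is that it cannot be interpreted until the drops and the analysed set are stated.

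**What to change.** Leave the clinical withdrawal rule as it is.

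1. In all children re-randomised to maintenance, report treatment failure (a drop for soiling or for discomfort above 4) as an outcome. Give counts by flush in use, period, sequence and reason, with data up to and including the event. A formal comparison between flushes is optional and should be labelled post hoc and low-powered. With an assumed 6, 10 or 15 children per sequence, a simulated permutation test of failures per child-week had power of about 27%, 61% and 79% at drop risks of 40% vs 10%, and 3%, 10% and 19% at 20% vs 10%. The counts would often be the main information.
2. State what counted as recurrence and which children entered the t-test. Label soiling and pain means among children still on study as descriptive, not as evidence of equal continence.
3. Reconcile "each child receiving both treatments in both interventional phases of the study" in Statistical Analysis with the entry gate in High Volume Regimen and Low Volume Regimen and the drop rule in Regimen Maintenance Phase, or state that no child was gated out or dropped. If that is so, one sentence closes the point.

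The cost is a little extra analysis and some wording, with no new patients or procedures. The events should already be on record, since outcomes were logged daily and "The parent was requested to call if the child was having accidents, discomfort greater than a 4 on the WBFPRS". The drawback is limited power.

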The high-volume regimen consisted of normal saline flush at a starting dose of 10mL/kg infused every other day and adjusted by flush volume and frequency of administration until stability of target outcomes was achieved. Notification of any fecal soiling resulted in an additional 5 mL/kg volume adjustment with a subsequent increase in administration frequency, if needed, so as not to exceed a maximum dose of 500 mL administered daily for a child under five years of age and 1000 mL administered daily for a child over 5 years of age. If the child could not achieve continence on the maximum dose and had not been trialed on the alternate therapy, they were trialed on USP glycerin but did not proceed to the maintenance phase of the study. If the child experienced side effects greater

than 4 on the WBFPRS at the starting saline dose, flush volume was incrementally decreased as needed by 2.5 mL/kg to the lowest dose of 5 mL/kg. The goal of the dosing phase was to identify the lowest effective dose and flushing frequency that resulted in continence with minimal side effects. If the dose required to minimize side effects resulted in fecal soiling or the child had side effects greater than 4 on the WBFPRS at the lowest flush dose, and had not been trialed on the alternate therapy, they were trialed on USP glycerin but did not proceed to the maintenance phase of the study.

Low Volume Regimen

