The low volume regimen consisted of USP glycerin diluted in normal saline instilled through the low-profile device starting on a dose of 20 mL of USP glycerin mixed in >20 mL of saline and adjusted by flush volume and frequency of administration until stability of target outcomes was achieved. The saline served as a diluent and was mixed at a sufficient dose to allow easy infusion of the solution through the ACE access tubing. Notification of any fecal soiling resulted in the addition of 5 to 10 mL with subsequent increase in frequency of administration, if needed, so as not to exceed 50 mL of USP glycerin administered daily. If the child could not achieve continence on the maximum dose and had not been trialed on the alternate therapy, they were trialed on high volume normal saline but did not proceed to the maintenance phase of the study. If the child experienced side effects greater than 4 on the WBFPRS at the starting USP glycerin dose, flush volume was incrementally decreased as needed by 5 mL increments to the lowest dose of 5 mL. The goal of the dosing phase was to identify the lowest effective dose and flushing frequency that resulted in continence with minimal side effects. If the dose required to minimize side effects resulted in fecal soiling or the child had side effects greater than 4 on the WBFPRS at the lowest flush dose, and had not been trialed on the alternate therapy, they were trialed on normal saline but did not proceed to the maintenance phase of the study.

Optimal Dose Regimen

Following optimal dose determination, the child was maintained on that volume and administration frequency for at least 2 weeks. A clinic visit was scheduled once the above criteria had been met. At that visit, the child was flushed at the optimal dose, labs were drawn, a stool sample collected, the procedure for the next regimen was reviewed with the parent and child, and procedural fidelity was ascertained.

Regimen Maintenance Phase

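### Dropping children for recurrent soiling or discomfort in maintenance removes first-treatment failures from the crossover comparison and shrinks any true difference in failure

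*Combined protocol and SAP*

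**What the plan says.** All references are to the combined protocol and SAP.

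- **Measures.** Postoperative outcomes were "obtained daily throughout all phases of the dosing and maintenance phases and included the number of episodes of fecal soiling per day". Abdominal pain and pain associated with flush administration were recorded over the same phases.
- **High Volume Regimen and Low Volume Regimen.** A child who fails the first regimen in dosing is still tried on the other but goes no further. After failure on saline, "they were trialed on USP glycerin but did not proceed to the maintenance phase of the study". After failure on glycerin, "they were trialed on high volume normal saline but did not proceed to the maintenance phase of the study".
- **Regimen Maintenance Phase.** After dosing, "patients were randomized for a second time to either a saline-glycerin-saline or a glycerin-saline-glycerin sequence". The periods last 4, 4 and 2 weeks, and the second treatment starts only after the first has been given and withdrawn. The exit rule is "If the child experienced recurrence of fecal incontinence or discomfort greater than a 4 on the pain scale, they were dropped from the study". No switch to the other regimen is described for a dropped child.
- **Statistical Analysis.** Dosing and maintenance are each described as a two-treatment crossover "with each child receiving both treatments in both interventional phases of the study". The test is a two-tailed, two-sample pooled-variance t-test at 0.05, justified by the statement "A cross-over design compares two treatment sequences; therefore, the groups are independent". The section does not define the per-child quantity tested, an analysis set, a failure endpoint or the handling of dropped children.

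**The concern.** The events that end a child's participation in maintenance are the events that would show one regimen to be worse than the other. Dosing lets a child who fails one regimen try the other; maintenance does not. A child who fails in the first 4 weeks therefore has a maintenance record on one regimen only and cannot enter a within-child contrast.

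For children who entered maintenance, the statement that each received both treatments is true only if nobody was dropped in the first period. If some were, the regimen that loses continence or tolerability more often loses more of its failures from the comparison, and the two regimens look more alike than they are.

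**Working it through.** The plan gives no sample size, failure rate or drop count, so there is no figure of its own to reproduce. The check shows what the drop rule does to the standard crossover contrast under assumed rates.

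**Inputs from the plan:** two sequences, two 4-week periods before the two-week reintroduction, and removal on failure. The exit sentence follows the description of the third period. I read it as covering all of maintenance, because the next sentence contrasts it with completing that phase.

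**Assumed:** 1:1 sequences, no period effect, 4-week failure probabilities pS (saline) and pG (glycerin), and probability p11 that a child would fail both. Making saline the worse regimen is arbitrary; reversing the roles only changes the sign.

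**Within-child contrast.** A pair exists only if the child does not fail the first treatment. Among pairs, the saline-first sequence shows glycerin failures with probability (pG − p11)/(1 − pS). The glycerin-first sequence shows saline failures with probability (pS − p11)/(1 − pG). The estimate of pS − pG is

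½ × [(pS − p11)/(1 − pG) − (pG − p11)/(1 − pS)].

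| pS, pG | Failures within child | p11 | True difference | Estimate | Share kept |
|---|---|---|---|---|---|
| 0.30, 0.10 | independent | 0.03 | 0.20 | ½(0.27/0.90 − 0.07/0.70) = 0.100 | 50% |
| 0.30, 0.10 | nested | 0.10 | 0.20 | ½(0.20/0.90 − 0/0.70) = 0.111 | 56% |
| 0.40, 0.20 | independent | 0.08 | 0.20 | ½(0.32/0.80 − 0.12/0.60) = 0.100 | 50% |
| 0.40, 0.20 | nested | 0.20 | 0.20 | ½(0.20/0.80 − 0/0.60) = 0.125 | 63% |
| 0.20, 0.20 | either | 0.04 or 0.20 | 0 | 0 | – |

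The last row shows that this is attenuation; it does not create a difference where none exists.

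Children with no pair make up (0.30 + 0.10)/2 = 20% in the first setting and (0.40 + 0.20)/2 = 30% in the second. For 30% against 10% with independent failures, first-period failures are 0.20 and second-period failures are ½(0.70 × 0.10 + 0.90 × 0.30) = 0.17. So 0.20/0.37 = 54% of failures over the two periods go uncounted.

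**Failure score.** Score +1 for a drop on the first treatment, −1 for a drop on the second, 0 for neither. The mean score is pS − (pG − p11) in saline-first children and pG − (pS − p11) in glycerin-first children. Half the difference is

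½ × {[pS − (pG − p11)] − [pG − (pS − p11)]} = pS − pG,

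whatever p11 is. For 30% against 10%:
- independent: ½[(0.30 − 0.07) − (0.10 − 0.27)] = ½(0.23 + 0.17) = 0.20
- nested: ½[(0.30 − 0) − (0.10 − 0.20)] = ½(0.30 + 0.10) = 0.20

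With a period effect the score estimates the average of the two periods' differences. If the second-period hazard is halved and failures are independent, the second-period difference is (1 − √0.70) − (1 − √0.90) = 0.112, and the score gives (0.200 + 0.112)/2 = 0.156.

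**Small samples** (simulation, 4,000 trials per setting, correlated failures, assumed n of 12, 20 and 30). The t-test on the score had type I error 0.038 to 0.059; the permutation version had 0.005 to 0.020. At n = 20 and 10% against 30%, power was 32% for the score t-test, 19% for the permutation version and 11% for a t-test on children with both values.

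**The case against.** **Perhaps nobody was dropped.** The document is written in the past tense about a finished study, and its statement that each child received both treatments may be a plain report of fact. That stands as a possibility, and there would then be no bias. No counts are given either way. A reader might infer that this trial's maintenance results are biased; the documents do not show that.

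**The faulted analysis is not spelled out.** This also stands: the quantity entering the t-test is undefined. Pooling values by treatment would lose almost nothing. For 30% against 10% with independent failures it gives (0.30 + 0.27)/1.90 − (0.10 + 0.07)/1.70 = 0.30 − 0.10 = 0.200. With nested failures it gives 0.50/1.90 − 0.10/1.70 = 0.204. But pooling puts the same child in both groups, which does not fit the plan's argument that the groups are independent because sequences are compared. That argument points to one value per child, compared between sequences. A first-period comparison would also count first-treatment failures, but it is not within-child and is not described.

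**The graphs would show a drop.** Correct. Daily data up to the drop exist and single-case analysis is a main method. A reader might take "Reported data was limited to the results from numeric descriptive and inferential analysis that could be adapted to the Clinicaltrials.gov format" to mean that failures are hidden from the study's analysis. It is a limit on what was posted in the registry's format, no more.

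**Maintenance failure is not a named endpoint.** True. The Study design section stresses minimal dose and frequency with fewer side effects while continent. Soiling and pain are nevertheless listed outcomes throughout maintenance, and that phase is to be analysed as a crossover.

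**The wording may be narrower than it looks.** A reader might infer that completers cannot have pain above 4 or any soiling on either regimen. The first needs discomfort in the exit rule to cover all pain, yet the Measures section separates abdominal from flush-related pain and ties its call-in threshold to the flush. The second needs one episode to count as a recurrence, and no threshold is stated.

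**Conclusion.** The point holds for one comparison: within-child differences in maintenance, compared between sequences. The exit rule and that analysis together exclude every child who fails on the first maintenance treatment, and a true difference in failure shrinks to 50% to 63% of its value at the assumed rates of 30% against 10% or 40% against 20%. This rests on 1:1 sequences, no period effect, the exit rule applying throughout maintenance, and failure patterns from independent to nested. The percentages illustrate the mechanism and are not estimates for this trial.

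The bias is zero if no child was dropped or if the regimens fail equally often. No bias is claimed in the single-case graphs, dosing-phase data, dose, frequency, electrolytes or calprotectin. It should be corrected in the analysis text and the report; confidence that it affected this trial's results is limited by the missing counts.

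**What to change.** 1. Analyse every child randomised the second time. Over the two 4-week periods, score +1 if dropped for soiling or pain above 4 on the first treatment, −1 if on the second, 0 if neither. Compare the score between sequences with the pooled t-test already planned, and give an exact permutation p-value beside it. Half the difference in means estimates the difference in 4-week failure. Repeat for soiling and pain separately.
2. Label this analysis post hoc if it is added after the data are known.
3. Report failures in the two-week reintroduction separately, because including them would give the first treatment 4 + 2 = 6 weeks against 4.
4. Define recurrence, and say which pain the discomfort criterion covers.
5. Report drops by regimen, period and reason, and children not entering maintenance by regimen.
6. State that maintenance results apply to children continent on both regimens in dosing.
7. If no child was dropped, say so; that settles the bias question.

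The cost is a few sentences and one derived variable from data already recorded. The score is coarse: it records failed or not and discards the daily counts. Power is low in a small sample (32% at an assumed n of 20), and the permutation p-value is conservative. The counts in step 5 are informative whatever the test shows.
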